4. METHODOLOGY

4.1. Study design: A prospectively study with clinical trials, 12 months follow up.

4.2. Subject: 30 patients with hypercholesterolemia (LDL-C), stage 3-4 Chronic Kidney Disease, not receiving dialysis and 30 control participants (sex, age-matched)

4.2.1. Inclusion Criteria:

30 patients with following criteria

- CKD in the 3,4 stage (e-GFR: 15-60 ml/min/1.73 m²)
- Presence of proteinuric CKD defined as creatinine clearance >20 ml/min/1.73 m² combined with urinary protein excretion rate >0.3 g/24 h
- LDL cholesterol concentration > 100 mg/dl (2,59 mmol/l)
- Age:
 - + ≥ 50 years old but not treated with chronic dialysis or kidney transplantation
 - + In adults aged 18-49 years with CKD but not treated with chronic dialysis or kidney transplantation, we suggest statin treatment in people with one or more of the following:
 - known coronary disease (myocardial infarction or coronary revascularization)
 - diabetes mellitus
 - prior ischemic stroke
 - estimated 10-year incidence of coronary death or non-fatal myocardial infarction > 10%

4.2.2. Exclusion Criteria

- In adults with dialysis-dependent CKD
- Heart failure (New York Heart Association class III or more)
- Previous or concomitant treatment with corticoids, statin, immunosuppressive agents, vitamin B6, B12, folate
- Pregnancy
- Patients who do not agree to participate the research
- Patients are unable to fully understand the purposes/risks of the study and to provide a written informed consent

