(1) Do different lipid-lowering drugs (simvastatin monotherapy and ezetimibe/simvastatin combination therapy) have a different impact on the lipid profile, oxidative stress indices, Tryptophan degradation?

(2) Does statin monotherapy or co-administration of ezetimibe ameliorate the renal dysfunction in CKD patients?

(3) How do lipid-lowering therapy effect on lipidemia disorders in patients with CKD by mechanism involved in oxidative stress and tryptophan?

(4) Are the unexpected effects on muscle problem and hepatic enzyme profile of long-term statin monotherapy and statin/ezetimibe combination therapy a big concern?

II. REVIEW OF RESEARCH LITERATURE

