2.12. Simvastatin

- Treat with statins for 1-2 weeks, up to 4-6 weeks, and maintain during long-term treatment.
- Simvastatin largely excreted in the feces. Approximately 10-15% of the drug excreted by the kidney
- Dosage is 5-80 mg/day, in the evening.
- No dosage adjustment is needed in the elderly
- **Contraindications of Simvastatin:**
 - + Active liver disease or unexplained persistent elevations of serum transaminases

- + Pregnancy and lactation
- + Concomitant administration of potent CYP3A4 inhibitors (e.g. itraconazole, ketoconazole, posaconazole, HIV protease inhibitors (e.g. nelfinavir), erythromycin, clarithromycin, telithromycin, and nefazodone)
- + Concomitant administration of gemfibrozil, ciclosporin, or danazol.
- **Unexpected effects of Simvastatin and how to manage unexpected effects**
 - + **Myopathy:** The risk of myopathy is related to dose. In a clinical trial of 41,413 patients treated with simvastatin, 24,747 patients (about 60%) with an average follow-up of at least 4 years, the incidence of myopathy was approximately 0.03%, 0.08% and 0, 61% at doses of 20, 40 and 80 mg/day, respectively.
 - If the patients have muscle aches, weakness or cramps, do CK test. If CK increases (> 5 times) discontinue treatment, re-assess levels within 5 to 7 days.
 - If the muscular symptoms are severe and cause daily discomfort, even if the CK levels are < 5 times normal, consider stopping treatment.
 - + **Elevated liver enzymes:** Continuous elevations (up to > 3 times) liver enzymes have occurred in some patients receiving simvastatin.
 - When simvastatin is discontinued, the level of transaminase usually decreases gradually down to the pre-treatment level.

+ **Diabetes Mellitus**

Some evidence suggests that statins as a class raise blood glucose and in some patients, at high risk of future diabetes, may produce a level of hyperglycemia where formal diabetes care is appropriate. This risk, however, is outweighed by the reduction in vascular risk with statins and therefore should not be a reason for stopping statin treatment.

+ Other side effects: Dizziness, fainting, fast or irregular heartbeat,...

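### The exclusion list in 4.2.2 omits five contraindications that 2.12 and 2.13 name, and the follow-up procedure in 4.6 does not call on the stopping rules in 2.12

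*Protocol*

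**What the plan says.** Section 4.5 gives simvastatin to every patient for 12 months: 40 mg alone in Group 1, and 20 mg or 40 mg with ezetimibe 10 mg in Groups 2 and 3.

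Section 2.12 lists four contraindications to simvastatin:

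- "Active liver disease or unexplained persistent elevations of serum transaminases"
- "Pregnancy and lactation"
- "Concomitant administration of potent CYP3A4 inhibitors"
- "Concomitant administration of gemfibrozil, ciclosporin, or danazol"

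Section 2.13 adds that ezetimibe should be avoided when liver failure is moderate or worse. Section 2.12 also gives management instructions, starting with "If the patients have muscle aches, weakness or cramps, do CK test". Treatment is to stop if CK rises more than 5 times, with re-assessment after 5 to 7 days. Stopping is to be considered when muscle symptoms are severe, even below that CK level. Both sections fall under the heading "II. REVIEW OF RESEARCH LITERATURE".

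The operative text is in section 4. The exclusions in 4.2.2 are dialysis dependence, heart failure of NYHA class III or worse, pregnancy, lack of agreement or of capacity to consent, and one drug item: "Previous or concomitant treatment with corticoids, statin, immunosuppressive agents, vitamin B6, B12, folate". Section 4.6 provides for a medical history and for CK, SGOT and SGPT at screening. It has treatment carry on at each follow-up visit, with muscle pain and other medication recorded. Section 5 repeats the three blood tests at 4, 8 and 12 months.

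**The concern.** Eligibility is decided by 4.2 and conduct by 4.6, and neither points back to 2.12 or 2.13. A site working from section 4 could randomise a patient with active liver disease, or one taking clarithromycin or gemfibrozil, without breaching a listed criterion. During follow-up, 4.6 asks staff to record muscle pain and other medication but attaches no action to either, or to a laboratory result.

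What is at stake is patient safety. It is also close to the trial's own questions: research question 4 opens "Are the unexpected effects on muscle problem and hepatic enzyme profile of long-term statin monotherapy" and goes on to ask the same of the combination.

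**Working it through.** The protocol has no figure to reproduce here. The check sets the contraindications against the exclusions, then the management rules against the follow-up procedure.

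**Step 1: contraindications against 4.2.2.** The three overlapping liver items (active liver disease, persistent transaminase elevation, liver failure) are merged into one.

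| Item in 2.12 or 2.13 | In 4.2.2? |
|---|---|
| Liver disease, persistent transaminase elevation, liver failure | No |
| Pregnancy | Yes, by name |
| Lactation | No |
| Potent CYP3A4 inhibitors | No |
| Gemfibrozil | No |
| Ciclosporin | Yes, by class (immunosuppressive agents) |
| Danazol | No |

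Covered: 2. Absent: 7 − 2 = 5.

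**Step 2: does the result depend on how items are counted?**

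- With the liver items kept separate there are 7 + 2 = 9 items, of which 9 − 2 = 7 are absent.
- By bullet there are 4 in 2.12 plus 1 in 2.13, so 5. Three are wholly absent (liver disease or transaminases, CYP3A4 inhibitors, liver failure), two are partly covered (pregnancy without lactation; ciclosporin without gemfibrozil or danazol), and none is fully covered.

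On each count the majority is missing.

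**Step 3: to whom do the items apply?** The simvastatin items apply to all 30 patients. The ezetimibe item applies to Groups 2 and 3, 10 + 10 = 20 patients.

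**Step 4: management rules against 4.6.**

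| Situation | Rule in 2.12 | Action in 4.6 |
|---|---|---|
| Muscle aches, weakness or cramps | Test CK | Record unexplained muscle pain |
| CK more than 5 times | Discontinue, re-assess in 5 to 7 days | None |
| Severe symptoms at lower CK | Consider stopping | None |
| Transaminases staying above 3 times | Described as having occurred; no instruction | None |
| Interacting drug started mid-trial | Contraindicated | Record non-study treatment |

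The first three rows have a rule in the protocol, but in a section that 4.6 does not cite. The fourth has no rule in the visible text. In the fifth, the contraindication is stated but not what to do about it. The multiples also need a reference value: the CK discontinuation rule states none, although the adjacent severe-symptom rule refers to normal, and the transaminase remark states none.

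**Step 5: how often might myopathy occur?** Section 2.12 quotes 0.03% at 20 mg and 0.08% at 40 mg, over an average follow-up of at least 4 years. Groups 1 and 3 take 40 mg (20 patients) and Group 2 takes 20 mg (10 patients):

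20 × 0.0008 + 10 × 0.0003 = 0.016 + 0.003 = 0.019 expected cases.

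This is only a rough guide. The follow-up behind those rates is longer than 12 months, and they do not describe contraindicated patients, who are the ones at issue.

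**The case against.** The best defence is that the muscle rules are already in the protocol, worded as instructions rather than as summaries of other studies. Section II also serves as a reference section: 2.2 defines the CKD stages and 2.14 the heart failure classes that section 4 uses, and the age rule in 4.2.1 follows 2.10 closely. A clinician who reads the whole protocol has the CK and severe-symptom rules, and the 4.6 line on continuing treatment can be taken as describing a routine visit.

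This stands. A reader might infer that the protocol has no stopping rules for muscle toxicity, or that 4.6 orders treatment to continue through a raised CK. The documents do not support either. For muscle effects the fault is where the rules sit, and the tension with 4.6.

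Other safeguards count too. Patients may ask for unscheduled visits (4.6). Section 2.3 says fibrates are contraindicated in renal failure. Section 2.13 asks for monitoring when simvastatin above 20 mg is combined with ezetimibe at GFR below 60, which describes Group 3. But neither section 2 statement is carried into 4.2.2 or cited in 4.6, and the screening check of other eligibility criteria in 4.6 does not say what they are.

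It is also tempting to size the gap by multiplying patients, visits and tests. That would count CK results for which 2.12 does give a rule, at least in symptomatic patients. For eligibility it would count those enrolled when the relevant number is those screened, which is not given. Such totals measure paperwork, not risk.

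Finally, the section numbering passes from 5 to 7, so safety text may exist outside the visible pages. Absence from 4.2.2 and 4.6 is certain; absence from the complete protocol is not.

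**Conclusion.** The point holds as a low-cost safety correction. Five of seven named contraindications are missing from 4.2.2, so applying that list as written can place a contraindicated patient on simvastatin. The count assumes that the liver items are merged and that the immunosuppressive class covers ciclosporin; without the second assumption it is six of seven. The CK and severe-symptom rules exist but are not linked to the follow-up procedure. The visible protocol gives no action for persistently raised transaminases.

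The number of patients affected cannot be stated, because the documents give no prevalence for the five items. Confirmed myopathy should be rare in 30 patients if the quoted rates apply. A reader might infer that the trial's results are compromised; nothing here supports that, since estimates, power and type I error do not depend on these rules.

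**What to change.** 1. **Section 4.2.2.** Add five exclusions: active liver disease or unexplained persistent transaminase elevation (including moderate or severe liver failure), lactation, potent CYP3A4 inhibitors, gemfibrozil and danazol. Check them before randomisation against medical history, drug history and screening SGOT and SGPT, with a transaminase cut-off set by the sponsor.
2. **Section 4.6, muscle.** Have treatment continue unless a 2.12 stopping rule is met, and restate the rules there: CK on muscle symptoms; discontinuation above 5 times a stated reference value, with re-assessment in 5 to 7 days; stopping considered for severe symptoms. Apply the CK threshold to scheduled draws as well, and say that this extends 2.12, which ties the test to symptoms.
3. **Section 4.6, liver.** Interrupt study drug if transaminases stay above 3 times a stated reference value. The multiple comes from 2.12; the action is new.
4. **Section 4.6, interacting drugs.** Tell patients to report any new medicine before starting it, and interrupt study drug while a contraindicated one is taken. A record made at visits four months apart would miss a short course of erythromycin or clarithromycin.

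The cost is a protocol amendment, a slightly smaller eligible pool and occasional unscheduled or repeat tests. The history, the scheduled SGOT, SGPT and CK draws and the non-study treatment record are already in 4.6 and section 5.

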4.2.3. Criteria for control

- 30 aged, sex-matched subject
- Do not have history of diabetes, hypertension, cardiovascular or cerebrovascular disease, renal failure, blood dyscrasias, cancer, retinal vascular disorders
- Current medication with vitamin B6, B12, or folic acid

4.3. Place:

- In Viet Nam: Internal examination room, internal department, Department of Biochemistry of Hue University Hospital.

- In Italy: Department of Biochemistry of Sassari University Hospital

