STUDY PROTOCOL

LIPID - LOWERING REGIMES IMPROVE OXIDATIVE STRESS, TRYPTOPHAN DEGRADATION IN HYPERCHOLESTEROLEMIA CKD PATIENTS

Date of review: 03th May, 2018

Brief Title:

**LIPID-LOWERING THERAPIES IN VIETNAMESE CHRONIC KIDNEY
DISEASE POPULATION**

I. BACKGROUND - ABSTRACT/SUMMARY STATEMENT OF THE RESEARCH PROJECT:

The prevalence of chronic kidney disease (CKD) in Vietnamese population is increasing along with hypertension and diabetes. 3.1% of the population diagnosed as CKD (stages 3-5) with positive findings in urine test (Ito et al., 2008). In CKD patient, cardiovascular disease (CVD) is the leading cause of mortality. Kidney Disease Statistics for the United States showed that the prevalence of CVD is 69.6 percent among person ages 66 and older who have CKD, compared to 34.7 percent among those who do not have CKD (Health, 2012).

The lipidemic disorder is one of the cardiovascular risk factors in CKD but it was not fully concerned. Highest cholesterol in CKD patient is the total or low-density lipoprotein (LDL).

A one-year prospective study of stage 3 or 4 CKD patients with dyslipidemia Siriraj Hospital showed that the percentage of patients with hypercholesterolemia was 78%, hypertriglyceridemia 54%, and low high-density lipoprotein-C 36% (Sangswang & Sriwijitkamol, 2015). Two-thirds of CKD patients with hyperlipidemia had mixed hyperlipidemia. Despite the high frequency of statin treatment, only one-third of CKD patients achieved the LDL-C goal (Sangswang & Sriwijitkamol, 2015). A question whether high-dose of statins monotherapy is more effective in LDL cholesterol lowering is still unclear, but high doses are associated with a high rate of hepatotoxicity, myopathy. Thus, we need to explore more advanced lipid-lowering therapies to manage dyslipidemia in patients with CKD.

Dyslipidemia has been proposed an independent risk factor in accelerating renal injury (Trevisan, Dodesini, & Lepore, 2006). Statin and Statin/ezetimibe were evidenced to prevent cardiovascular complications in CKD patient. Co-administration of ezetimibe the first time enhanced proteinuria-lowering effects of pitavastatin in non-diabetic CKD patients partly via a cholesterol-independent manner. Ezetimibe may have pleiotropic actions that could contribute to renoprotective properties of this lipid-lowering agent

(Nakamura, T., et al. (2010). However, it is still unclear if Statin and Statin/ezetimibe therapies can improve the renal function by proteinuria.

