2.1. Criteria for Chronic Kidney Disease

- Improving Global Outcomes 2012 Clinical Practice Guideline (KDIGO 2013) (Stevens, Levin, & for the Kidney Disease: Improving Global Outcomes Chronic Kidney Disease Guideline Development Work Group, 2013).

- Either of the following present for >3 months. Markers of kidney damage (one or more)

+ Albuminuria (AER \geq 30 mg/24 hours; ACR \geq 30 mg/g)

+ Urine sediment abnormalities Electrolyte and other abnormalities due to tubular disorders Abnormalities detected by histology Structural abnormalities detected by imaging

+ History of kidney transplantation

+ Decreased GFR GFR $<$ 60 ml/min/1.73 m² (GFR categories G3a–G5)

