4.6. Procedure

- Potentially eligible patients attended a screening visit in an internal examination room or internal department of Hue University Hospital for medical history and other eligibility criteria checked.

- Fasting blood samples will be taken for local laboratory assays lipid profile, proteinuria, urea and creatinine, creatine kinase, SGOT, SGPT, total blood count, total haemostasis test

- If the patient satisfies the including criteria, written informed consent obtained 30 enrolled patients will be randomized into 3 groups and will receive one of 3 lipid-lowering therapies at the baseline and continue for 12 months

Group 1: (10 participants) receive 40 mg/day simvastatin (patient No 1, 4, 7...)

Group 2: (10 participants) receive ezetimibe/simvastatin 10/20 mg/day: (patient No 2, 5, 8...)

Group 3: (10 participants) receive ezetimibe/simvastatin 10/40 mg/day: 10/40: (patient No 3, 6, 9...)

- Patients will follow the treatment for 12 months and will be seen in the study clinics for routine follow-up checks and blood test at 4, 8, and 12 months.

- At each follow-up time, study treatment will be continued, unexplained muscle pain and non-study treatment recorded.

Patients are asked for an unscheduled visit if they want to have any additional review.

- If patients are unable or unwilling to attend the follow-up checks, ask them if they have any serious adverse events.

- The blood samples will be sent to Biochemical Department of Sassari University for oxidative stress indices and Tryptophan degradation indices every 4 months.

5. Biochemical analysis

- Serum Creatinine, GFR, urine protein, lipid profile, SGOT, SGPT, CK (Total Cholesterol, LDL-C, HDL-C, TG): Will be done in Hue University hospital/Hue Central Hospital.

+ Total Cholesterol, LDL-C, HDL-C, and TG were measured by enzymatic methods using commercial kits (Boehringer-Mannheim, Mannheim, Germany): Patients must fast for at least 12 hours before the test

+ Serum CK levels were measured by using a fully automated biochemical analyzer (Abbot).

+ Proteinuria

+ Serum urea, creatinine

+ Total cells blood count

+ Total hemostasis test

[Time Frame: at baseline and 4, 8, 12 months of treatment]

- Serum concentrations of Oxidative stress indices (MDA, All/UA, Taurine), Trp degradation indices (Kyn, Trp, Kyn/Trp ratio): Will be done in Sassari University hospital.

MDA, All/UA ratio, taurine, Kyn, Trp were determined by capillary electrophoresis UV detection.

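### Controls are cleared of kidney disease by history alone, so unrecognised CKD can enter the control group and bias the patient-control comparison slightly toward no difference

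*Protocol*

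**What the plan says.** Protocol section 4.2.3 sets the control criteria. The only one that concerns the kidney is part of a history item: controls "Do not have history of diabetes, hypertension, cardiovascular or cerebrovascular disease, renal failure". No e-GFR, creatinine, proteinuria or albuminuria limit follows.

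Patients are classified by measurement. Section 4.2.1 requires "CKD in the 3,4 stage (e-GFR: 15-60 ml/min/1.73 m²" together with a urinary protein excretion above 0.3 g/24 h. Section 2.1, the protocol's definition of CKD, also rests on GFR and markers of kidney damage.

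Section 5 lists "Serum Creatinine, GFR, urine protein, lipid profile, SGOT, SGPT, CK" among the local tests, but times them by months of treatment. The screening visit in section 4.6 is likewise written for patients: "Potentially eligible patients attended a screening visit in an internal examination room or internal department". Neither section schedules a kidney test for controls or excludes a control on a result.

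The SAP compares mean laboratory results of patients and controls by one-way ANOVA or Student's t-test, so some control laboratory results are expected.

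**The concern.** The two sides of the comparison are classified by different standards. Early CKD can be silent, and a history question cannot find what was never diagnosed. The term used is also narrow on one reading: the stage table in section 2.2 speaks of failure only for stage 5 and describes stage 3 as a moderate reduction in function. A person with known stage 3 disease could then truthfully report no renal failure.

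The markers being compared are those the protocol itself ties to kidney disease. Section 2.4 cites an inverse relation between oxidative stress and e-GFR, and sections I and 2.5 link tryptophan degradation and oxidative status to CKD. A control with CKD would therefore tend to move the control mean toward the patients and widen the control spread. Once the assays have been run and compared, removing such a control becomes a post hoc decision.

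**Working it through.** The documents give no effect size, SD or power for the comparison of 30 patients with 30 controls, so there is no planned figure to reproduce.

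**Inputs**
- Controls: n = 30 (Protocol 4.2 and 4.2.3).
- Share p of eligible controls with undetected CKD: not given. The nearest figure is in the Background: "3.1% of the population diagnosed as CKD (stages 3-5) with positive findings in urine test". It describes the general population, so p is varied from 1% to 10%; both ends are assumptions.
- Two-sided alpha of 0.05: assumed, because the SAP states none for its comparisons.

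**Step 1: how many controls.** Expected number = 30p. Chance of at least one = 1 − (1 − p)^30.

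**Step 2: how much dilution.** If an affected control lies a fraction f of the way from the true control mean to the patient mean, the expected difference shrinks by p × f. With f = 1 (affected controls resemble the patients fully) the shrinkage is p, which is the upper bound as long as undetected cases are no more abnormal than the patients.

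| p | Expected of 30 | Chance of ≥ 1 | Shrinkage, f = 1 | Shrinkage, f = 0.5 |
|---|---|---|---|---|
| 1% | 0.3 | 1 − 0.99^30 = 26% | 1% | 0.5% |
| 3.1% | 0.93 | 1 − 0.969^30 = 61% | 3.1% | 1.6% |
| 10% | 3.0 | 1 − 0.90^30 = 96% | 10% | 5% |

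These are averages. In a realised sample each affected control is 1/30 = 3.3% of the group.

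**Step 3: effect on power, with f = 1.** For a true standardised difference d, the observed difference is d(1 − p) and the control variance rises to 1 + p(1 − p)d². With s² the mean of the two group variances, power = Φ[d(1 − p) / (s√(2/30)) − 1.96]. Two values of d are assumed: 0.74, close to the 0.72 SD detectable with 80% power at 30 per group, and 0.5.

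| d | Clean | p = 1% | p = 3.1% | p = 10% |
|---|---|---|---|---|
| 0.74 | 81.8% | 80.9% | 79.0% | 72.2% |
| 0.5 | 49.1% | 48.2% | 46.5% | 41.0% |

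Under this model the widening of the control spread is slight: at p = 10% and d = 0.74 the control variance is 1 + 0.09 × 0.5476 = 1.049. Nearly all of the loss comes from the smaller difference.

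**The case against.** The strongest objection is to the size. The 3.1% describes people in the general population with diagnosed stage 3-5 disease; what matters here is undiagnosed disease in people already cleared of known diabetes, hypertension, and cardiovascular or cerebrovascular disease. The Background itself ties the rise in CKD to hypertension and diabetes, so these exclusions should lower the share. Age matching to a patient group that may be largely 50 or older could raise it. The documents settle neither effect, and 10% has no basis in them. This stands: 3.1% is a reference point, not an estimate, and the range must extend below it.

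Second, a patient must combine reduced e-GFR, proteinuria and raised LDL-C. A silent case without diabetes or hypertension need not look like that, so shrinkage equal to p is an upper bound. This also stands. A reader might infer that one severe case would badly inflate the control SD, but the documents give no variance or skewness to support that, and a severe case with no renal history is the least likely kind.

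Third, the bias is toward no difference and so would not create a false patient-control difference. The objectives in section 3 and the research questions concern treatment, and none mentions controls. That the comparison comes first in the SAP is listing order, not stated priority.

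Fourth, the term renal failure is not defined for this purpose, and sections 2.3 and 2.4 use it more loosely than the stage table does. Investigators may apply it broadly. That would help with known stage 3 disease, but not with unrecognised disease.

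Finally, the test list might suggest that an available check is being left unused. The documents do not support that: the tests are written for patients, and none is scheduled for controls.

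**Conclusion.** The gap is real and minor. Section 4.2.3 does not exclude unrecognised CKD, and no other section closes the gap. The likely consequence is a small bias toward no difference in the patient-control comparison: a shrinkage of at most 1% to 10% on average over an assumed 1% to 10% of affected controls, and half that if affected controls lie midway to the patient mean. At 3.1% the power loss is under 3 percentage points for the two differences examined. These figures rest on an assumed share, an assumed alpha, and undetected disease no worse than the patients' disease.

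Two stronger readings should be resisted. A reader might infer that the trial's treatment conclusions are at risk; they are not, because the comparison of the three regimens and the within-patient changes use no controls. A reader might also take 3% to 10% as the expected attenuation; the documents do not give the share needed to say so.

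**What to change.** Add to section 4.2.3 that each control has serum creatinine with e-GFR and urine protein measured locally before the oxidative stress and tryptophan assays, and is eligible only with e-GFR of at least 60 ml/min/1.73 m² and urine protein or albumin below a cut-off stated in advance. The protocol already contains two candidates: the ACR limit of 30 mg/g in section 2.1 and the 0.3 g/24 h limit in section 4.2.1. The first needs an albumin measurement, which section 5 does not name; the second needs a 24-hour excretion figure. A control who fails is replaced by the next matched person, and the number replaced is reported.

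Describe this as a single-sample screen. It does not apply the full section 2.1 definition, which requires an abnormality lasting more than 3 months.

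The cost is one creatinine and one urine test for each control, including replacements, and probably zero to three replacements. Sections 4.6 and 5 must schedule the tests for controls explicitly, since both are now written for patients. No treatment, randomisation or analysis method changes.
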